#### Primary population of interest

The primary population of interest will be young people aged 11-18 referred to their Local Authorities for support and at medium to high risk of contextual harm.

Table 5 provides information about the number of young people and teams, and their distribution across treated and control groups, which were used to perform the power calculations. These numbers reflect the best information available at the time of writing, drawn from the Local Authorities' plans in terms of teams and expected numbers of participants in each team, before the trial started (sample A) and when the decision to extend the recruitment period was considered (Sample B).

Sample A reflects the size and composition of the final sample as estimated before the trial started. It totals 1857 young people across 138 teams.

Sample B reflects the size and composition of the final sample as re-estimated as of January 2025. It totals 1563 young people across 132 teams. This number was re-estimated based on recruitment to date and new information from Local Authorities about the number of young people they would expect to recruit if the recruitment period was extended to the end of February 2025.

		Sample A (1.0 original version)	Sample B (1.1 January 2025 update)
Average cluster size (if clustered)		Average number of participants per cluster (team): 13	Average number of participants per cluster (team): 11.8
Number of clusters (teams)	Intervention	70	83
	Control	70	49
	Total	138	132
Number of participants	Intervention	960	937
	Control	897	626
	Total	1857	1563

#### Table 5: Structure of the two datasets used to perform power calculations

Although randomisation during the efficacy phase allocates teams to training and control on a 50-50 basis, legacy randomisation from the Home Office and pilot phases means more teams are trained than control. The power calculations reported above account for this imbalance.

Our power calculations account for a 30% attrition rate. This attrition rate is calculated based on all participants ever recruited in randomised teams in the pilot and efficacy trials (regardless of not they collected any endline data).

Table 6 report the MDE estimated using the simulation methodology described above, under the below assumptions about power, significance level and the type of test we want to perform and under different assumptions about the attrition rate and about whether Local Authority fixed effects are controlled for in the regression. Note that, when we revised the expected sample size in January 2025, we also revised our assumptions about the ICC and mean of the baseline based on estimates of these parameters in the baseline sample recruited during efficacy, which we deemed more reliable than the pilot sample due to its much greater size.

These assumptions turned out to be less conservative than those made when we initially ran power calculations: the ICC was lower (0.09 as opposed to 0.12) and the mean of the primary outcome variable was higher (0.6 as opposed to 0.3). This meant that, even though the revised sample size in scenario 2 is lower than the initial sample size in scenario 1 the MDE is slightly lower (22% instead of 24%).

Table 6: Minimum Detectable Effect on primary outcome (binary indicator for high to very high range of conduct problems) under the assumption we do not control for lagged outcome in the larger dataset

Scenario	Scenario 1: Sample A with original priors for simulation parameters (1.0 original version)	Scenario 2: Sample B with revised priors for simulation parameters (1.1 January 2025 update)
Alpha 	0.05	0.05
Power	0.8	0.8

<sup>11 Please adjust as necessary for trials with multiple primary outcomes, 3-arm trials, etc., when a Bonferroni correction is used to account for family-wise errors.

One-sided or two-sided?	Two-sided	Two-sided
ІСС	0.12	0.09
Mean of the primary outcome in control group	0.3	0.6
Minimum Detectable Impact on Binary score for scoring in high or very high range on conduct problems	MDE = 24% reduction in the mean of the primary outcome	MDE = 22% reduction in the mean of the primary outcome

#### Discussion of MDEs in the context of the pilot trial and of the literature

The power calculations in Table 6 above indicate that, under a 30% attrition rate and based on the best information we have at the beginning of the trial about key parameters (Scenario 1), we could detect with 80% power a minimum effect of 24% of baseline probability to be in the high to very high range of conduct problems in the sample expected based on information provided by Local Authorities before the start of the trial (whereby 138 teams recruit 1857 young people). Of a 0.3 mean probability to be in the high to very high range of conduct problems, this would be equivalent to a reduction of 0.072 percentage points.

Revised power calculations based on the updated values for the simulation parameters as of January 2025 (Scenario 2) indicate that we could detect with 80% power a minimum effect of 22% of baseline probability to be in the high to very high range of conduct problems. For a 0.6 mean probability to be in the high to very high range of conduct problems, this would be equivalent to a reduction of 10.8 percentage points.

Under both Scenario 1 and Scenario 2, the MDE is within the range of impacts suggested by the endline data, well below the effects of CBT interventions on externalising behaviours, such as Attention Deficit Hyperactivity Disorder, Conduct Disorder and Oppositional Defiant Disorder, which are reported in the literature and which range around 60-70% (Gaffney, Farrington and White, 2021). Given that Your Choice is implemented on a large scale and delivered by non-clinical practitioners, it would be reasonable to expect a lower impact than

<sup>12 Gaffney, H., Farrington, D. and White, H. (2021). "Cognitive Behavioural Therapy: YEF Toolkit technical report"

the impact of CBT interventions reported in most of the literature. Yet, an effect size of 22% or 24% reduction (or a third or the impact sizes reported in the literature) still seem within the range of reasonable effects to expect from the Your Choice intervention.

#### Analysis

All codes and data needed to replicate the results from the efficacy trial will be provided. In preparing these replication materials, we will follow standard guidelines set out by the American Economic Association (American Economic Association (aeaweb.org).

The level of analysis for the core analysis will be the individual young person. The parameter that we will estimate in our main analysis with be an Intention-to-Treat (ITT) treatment effect measuring the effect on a young person's primary and secondary outcomes of being supported with a team that has trained in Your Choice (as opposed to a team that has not trained in Your Choice). The main Intention-to-Treat (ITT) specification related to our primary and secondary outcomes will be a linear regression, where we will control for baseline values of the outcome and baseline characteristics of the young person and/or their team that present statistically significant imbalances at baseline. In line with De Chaisemartin and Ramirez-Cueller (2022), we will present specifications with and without strata fixed effects. Some of the secondary analysis will be at the level of the meetings of the young-person and practitioner, and we will also consider some outcomes at the practitioner level – such as their assessment of the young person's needs and risks.

All methods were determined a priori and given what we have learned during the pilot phase.

We will use STATA version 16 or higher for the analysis.

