#### **Analysis**

Our primary analysis uses only randomised teams during the Home Office, pilot and efficacy phases. It will involve various steps.

Step 1. Thorough check that the group of young people assigned to Your Choice appear to come from the same population as those assigned to the control group along many observed variables describing demographic characteristics (e.g. gender, age, ethnicity, etc), main activity at baseline (education or training, employment, other), whether looked after, special education needs, primary needs for Local Authority support (e.g. abuse, disability, family acute stress, etc), various measures observed in the baseline youth survey including SDQ scores and self-reported risk assessment, practitioner risk assessment from baseline practitioner questionnaire. We will also check that the distribution of services to which young people have been assigned look balanced across experimental arms. All subsequent analysis addressing the key research questions set out earlier in this document must rely on a good understanding of the comparability between the treated and control groups.

Step 2. Thorough check of the delivery of Your Choice in contrast with BAU, revealing the extent to which the programme effectively changes interactions between the youth workers and young people and characterising the intensity of treatment for different groups. Specifically, we will check that young people assigned to Your Choice received an intensive schedule of meetings with content that is specific to the programme (hence matching the Your Choice protocol), while young people assigned to the control teams did not. Again, all subsequent analysis and interpretation of findings must rely on a good understanding of what the programme delivers in comparison with BAU.

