Step 3. Main analysis, which will be a linear probability model to measure the impact of Your Choice on an indicator for high to very high conduct problems (primary outcome). The regression will also control for the baseline outcome and any controls for which we find statistically significance imbalances in step 1, as well as Local Authority fixed effects. Standard errors will be clustered at the Local Authority level, following Chaisemartin and Ramirez-Cuellar (2022). Effects will be shown in percentage points and as a percent change relative to the baseline average frequency of young people in the high to very high range for this population. We will show the 95% confidence interval for the estimated effect. This analysis will directly address research question 1.

Step 4. Robustness analysis of estimated effects on primary outcome. This will involve estimating alternative versions of the primary regression model using a post-double selection

LASSO to identify variables that are related with both the treatment status and the primary outcome. We will consider relevant contextual, demographic, personal and environmental information as described in step 1. This analysis will provide further support for the findings in the main analysis (step 3).

Step 5. Steps 3 and 4 will be repeated for the secondary outcomes measuring whether the young person got arrested at any point during the 16 months following recruitment into Your Choice (PNC data), and risk assessments by the young person and practitioner at endline (survey completed at week 20 after recruitment). Effects on arrest probabilities will be shown in percentage points and as a percent change relative to frequency of arrests among the control group over the same period. Effects on risk levels will be shown in standard deviation units. Standard errors will be clustered at the local authority level and we will show the 95% confidence interval for the estimated effect. This analysis will address research question 2.

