*Wellbeing*: The Short Warwick–Edinburgh Mental Well-being Scale (SWEMWBS). Part of the endline young person questionnaire, which is administered at some point between weeks 14 and 20 after recruitment.

*Emotional self-regulation*: Trait Emotional Intelligence Questionnaire – Adolescent Short Form (TEIQUE-ASF) – Self regulation subscale. Part of the endline young person questionnaire, administered at week 20 after recruitment.

Social connectedness: Social Connectedness Scale – Revised (SCS-R). Part of the endline young person questionnaire, administered at week 20 after recruitment.

Internalising behaviours: emotional difficulties and peer difficulties subscales of the SDQ measured at baseline and endline as part of the participant's surveys administered following recruitment and at week 20 after recruitment respectively.

*Hyperactivity*: hyperactivity subscale of the SDQ measured at baseline and endline as part of the participant's surveys administered following recruitment and at week 20 after recruitment respectively.

*Prosocial behaviours*: Strength and Difficulties prosocial behaviour subscale measured at baseline and endline as part of the participant's surveys administered following recruitment and at week 20 after recruitment respectively.

*Prosocial identity*: Pro-social Identity Scale (PIDS) measured at baseline and endline as part of the participant's surveys administered following

		recruitment and at week 20 after recruitment respectively.	
	variable	Conduct problems	
Baseline for primary outcome	measure (instrument, scale, source)	Indicator for scoring in the high or very high range of conduct problems scale from the Strengths and Difficulties Questionnaires.	
		Measured as part of the baseline participant's survey, administered in week 1 after recruitment, before the start of Your Choice.	
	variable	Social connectedness score, internalising behaviour, hyperactivity, prosocial behaviour and prosocial identity, self-reported and practitioner-reported perceptions of young person's safety.	
	measure (instrument, scale, source)	All measured as part of the baseline participant's survey, administered in week 1 after recruitment, before the start of Your Choice.	
Baseline for secondary		Social connectedness: The Social Connectedness Scale – Revised (SCS-R), survey of young person following consent before Your Choice starts (in some cases, some form of BAU work/support will have already been taking place).	

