#### Primary outcome analysis

We will estimate the Intention-to-Treat (ITT) effect by estimating the following equation for young person i will be of the form:

$$Y_{i1} = \beta_0 + \beta_1 D_i + \beta_2 X_i + \beta_3 Y_{i0} + strata fixed effects + u_i$$

where  $Y_{i1}$  is the primary outcome of interest, which is an indicator that takes the value 1 if the young person scores in the high to very high conduct problems range and 0 otherwise, and  $Y_{i0}$  is the baseline value for that same outcome,  $D_i$  is an indicator for treatment assignment,  $X_i$  are any baseline characteristics of the young person and/or their team for which we find statistically significant imbalances between treated and control groups, and  $u_i$ is an error term. Standard errors will be clustered at the Local Authority level, following Chaisemartin and Ramirez-Cuellar (2022).

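### The primary model's covariates are left to baseline significance tests and baseline conduct enters only as a yes/no indicator, so the headline specification is not fixed and precision is given away

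*SAP*

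**What the plan says.** **Covariates.** Step 3 of the protocol's Analysis section adjusts the primary regression for the baseline outcome, LA fixed effects and "any controls for which we find statistically significance imbalances in step 1". Step 1 compares the arms "along many observed variables describing demographic characteristics", main activity, looked-after status, special educational needs (SEN), primary need, SDQ scores and risk assessments. The SAP keeps the rule. Its Analysis section adjusts for "baseline characteristics of the young person and/or their team that present statistically significant imbalances at baseline", and the Primary outcome analysis section defines X as "any baseline characteristics of the young person and/or their team for which we find statistically significant imbalances between treated and control groups".

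**Baseline conduct.** In the SAP's primary equation the lagged term "is the baseline value for that same outcome", and the outcome there is binary. The Design overview confirms the baseline measure: "Indicator for scoring in the high or very high range of conduct problems scale from the Strengths and Difficulties Questionnaires". The Data section of the protocol shows that the SDQ itself is administered at baseline.

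**Other models.** The SAP's Robustness checks plan a model with treatment and strata effects only, a post-double-selection LASSO model, and probit or logit versions. All are secondary to the headline model.

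**Pre-specification.** The SAP's Analysis section also states: "All methods were determined a priori and given what we have learned during the pilot phase".

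**The concern.** A significance test of baseline imbalance measures how unlikely an arm difference is. It does not measure how strongly the variable predicts the outcome. A strong predictor that is balanced stays out and its precision is lost. A weak one that crosses the threshold goes in. A confounder with a relevant but non-significant difference is not adjusted for.

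The rule is also incomplete. It names no candidate list, test, level or treatment of clustering. The SAP promises balance tables for two samples (everyone recruited, and those with endline data) without saying which one triggers inclusion. Team characteristics are eligible in the primary model but are not mentioned in the secondary one. Step 3 of the protocol points to imbalances in step 1, while Step 6 points to steps 1 and 2.

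The yes/no baseline treats a young person just under the cut-off like one with no conduct problems. Recruitment was lower and attrition higher than expected, and the recruitment period was extended, so precision available from data already collected matters.

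**Working it through.** **1. The plan's own figure.** SAP Table 6, Scenario 1, gives a minimum detectable effect (MDE) of 24% of a mean of 0.3, without the lagged outcome.
- Analysed sample: 1,678 × 0.7 + 83 ≈ 1,258.
- Treated share a = 960/1,761 = 0.545 (protocol Table 5).
- With the LA effect absorbed by fixed effects, MDE = (1.960 + 0.842) × √[0.3 × 0.7 / (1,258 × 0.545 × 0.455)] = 0.0727, and 0.0727/0.3 = 24.2%.

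The 24% reproduces.

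**2. Value of the continuous score.** Let the latent baseline and endline scores be standard bivariate normal with r² = 1 − residual variance, both cut at c to give prevalence p, with P₁₁ the probability of exceeding the cut at both times. For the binary endline outcome:
- indicator only: R² = (P₁₁ − p²)² / [p(1−p)]²
- score only: R² = r²φ(c)² / [p(1−p)]
- both: R² from the two-predictor linear projection
- equivalent extra participants = (1 − R²ind)/(1 − R²both) − 1
- SE reduction = 1 − √[(1 − R²both)/(1 − R²ind)]

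The documents give two residual values: variance 0.6 (protocol Table 7, r² = 0.4) and SD 0.5 (protocol Table 4, variance 0.25, r² = 0.75). They conflict, so both are used. r² = 0.2 is added as an assumed weaker case. Prevalences are those in SAP Table 4.

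| r² | p | R² indicator | R² score | R² both | Extra participants, both vs indicator | SE reduction |
|---|---|---|---|---|---|---|
| 0.4 | 0.3 | 0.177 | 0.230 | 0.238 | 8.0% | 3.8% |
| 0.4 | 0.6 | 0.187 | 0.249 | 0.253 | 8.8% | 4.1% |
| 0.2 | 0.3 | 0.079 | 0.115 | 0.116 | 4.3% | 2.1% |
| 0.2 | 0.6 | 0.085 | 0.124 | 0.125 | 4.5% | 2.2% |
| 0.75 | 0.3 | 0.429 | 0.432 | 0.490 | 11.8% | 5.4% |
| 0.75 | 0.6 | 0.441 | 0.466 | 0.508 | 13.6% | 6.2% |

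Replacing the indicator by the score, rather than adding it, gains less: 7.0% and 8.2% at r² = 0.4, and only 0.4% at r² = 0.75 with p = 0.3. That is why the fix keeps both terms.

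On the MDE scale (r² = 0.4, p = 0.3): 24% unadjusted; 24 × √(1 − 0.177) = 21.8% with the indicator; 24 × √(1 − 0.238) = 21.0% with both.

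**3. How often the rule fires by chance.** With k independent candidates tested at 5% and no true imbalance, P(at least one selected) = 1 − 0.95^k: 23% for k = 5, 40% for 10, 64% for 20 and 87% for 40. The plan gives neither k nor the level, so these are assumptions.

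**4. What the rule does to inference.** This was simulated with 500 replicates per setting, an assumed layout of 29 LAs and 132 teams, LA-clustered SEs and 20 candidate covariates assumed to explain 10% of latent variance.
- Type I error under the SAP rule was 4–7%, similar to the other models (Monte Carlo SE about 1 point), with no material bias.
- Power at mean 0.3 for a 24% reduction was 76–80% under the SAP rule and 81–83% with a fixed list of all 20 plus the continuous score.
- Power at mean 0.6 for a 16% reduction was 83–86% and 88–91% respectively.
- With a team-level covariate ICC of 0.05 and a balance test that ignores clustering, at least one covariate was selected in 83–89% of runs.

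**The case against.** **Imbalance here may be real.** Young people are not randomised. The protocol reports that some pilot allocators weighed potential benefit and perceived risk, and its Compliance section says non-random allocation and differential consent could not be told apart. On this view the rule is a bias-control step. That stands as a reason to adjust, and against deleting the rule. It does not justify significance as the criterion, because a confounder can matter without reaching it. It also means that the chance-selection figures, which assume no true imbalance, describe only part of the picture.

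**The robustness models cover it.** The simple model would expose dependence on the selected covariates. The continuous score could enter through the LASSO, or through X if SDQ scores proved imbalanced. This stands as partial mitigation, but none of it fixes the headline model.

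**More covariates could lose cases.** The protocol's risk register rates missing date of birth as highly likely and incomplete practitioner surveys as a medium risk. The SAP compares complete cases with multiple imputation for missing covariates but does not say how the headline model treats them. A complete-case headline model that lost 7–8% of cases (1 − 1/1.080 = 7.4%; 1 − 1/1.088 = 8.1%) would cancel the gain. This stands, and the fix must deal with it.

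**Larger gains might be inferred.** Pairing baseline prevalence 0.6 with endline 0.3 gives about 12% at r² = 0.4: (1 − 0.141)/(1 − 0.230) = 1.116. No scenario in the documents uses that pairing; SAP Scenario 1 has 0.3 and Scenario 2 has 0.6.

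**Conclusion.** The point holds as one of specification and efficiency. The headline model is not fixed in advance, it selects covariates on a criterion unrelated to prognosis, and it discards information in a score already collected. Adding the continuous score to the indicator is worth about 8–9% more participants under Table 7's residual variance, within a range of about 4% to 14% over the correlations considered. This rests on a bivariate-normal approximation with equal baseline and endline prevalence. The real subscale is discrete, so the figures are approximate. The power comparison also rests on the assumed 20 covariates and their 10% share of latent variance.

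Two stronger readings are not supported. A reader might infer that data-driven selection inflates the type I error or biases the estimate; the simulation found neither clearly. A reader might also infer that any imbalance is chance and that the rule should simply go; the documents themselves allow for selective allocation and consent.

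The change should be made, but the plan is not invalid without it.

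**What to change.** In Step 3 of the protocol's Analysis section, and in the SAP's Analysis and Primary outcome analysis sections:

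- **Fix the primary covariates now:** continuous baseline conduct score plus the baseline indicator, LA fixed effects, age, gender, ethnicity, SEN and baseline practitioner risk rating. Add those other Step 1 variables judged in advance to be likely drivers of allocation or consent, such as looked-after status and primary need.
- **State how missing covariate values are handled** in the headline model by a simple method, for example a missing indicator or mean imputation, so that no case with an outcome is dropped.
- **Report the balance table descriptively.** Move the imbalance-triggered model to a sensitivity analysis alongside post-double-selection LASSO. For that model, state the candidate list, the test, its level, its handling of clustering and the sample used.
- **Secondary SDQ outcomes:** where the binary version is analysed, adjust for the continuous baseline score as well.

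The cost is SAP and protocol wording and a few degrees of freedom. The variables are already part of the planned data collection.
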